4.7.3 Dataset

The observer, using a tablet application will record following data:

- (1) Activities. 22 activities were defined for our 2015 baseline study and are presented in the **appendix 1**. Activities are exclusives: a resident cannot do two activities at the same time.
- (2) **Circumstances.** The observers will record following circumstances for each activity. They are not exclusive: presence of the patient, usage of computer, usage of phone or smartphone, presence of one or more colleague.
- (3) Perturbation. Perturbation is a factor slowing or compromising the current activity. Perturbation begins with detection of the problem and ends with return to the index situation. They are exclusive: usage problem; missing information; missing people; communication conflict
- (4) **Timestamp.** Each time a resident starts a new activity or when circumstances change, a timestamp with precision up to the second is recorded. Delta between two timestamp defines the duration of an activity. At the end of the day, a timestamp "end of observation" is recorded.

4.7.4 Data management

The data from each observation shift will be saved in an Excel file, using a tablet with a dedicated application allowing recording of activities and settings in real-time. Each line in the text file will contain the task and the task start time, so that the task times flow continuously. The time spent on all occurrences of each task will be summed to generate the total time spent on each task for each subject. The final database will be saved in Stata format and hosted in one of the CHUV servers. All databases will be accessible by the investigators of the study only. The CHUV has implemented strict security policies regarding IT infrastructure and data protection, which are detailed in **appendix 2** and **3**. Paper and electronic data will be kept for a period of 10 years and then destroyed/erased according to the CHUV protocol.

4.8 Methods of minimizing bias

Based on literature and our previous study, we identified the following potential biases.

- (1) The observation bias (Hawthorne's effect) cannot be avoided. We will recruit observers among medical students, acting like other students in our ward. We will not communicate the day of observation to the resident. No contact between the observer and the resident will be allowed with the following exception: observer may occasionally ask the resident for precision about the current activity, if in any doubt about what he is doing.
- (2) Observers might misinterpret the current activity of a resident, occasionally or systematically. We will train observers with a standard video and blank observations. During a subsequent meeting, the observers will share their experiences and each dubious interpretation of activities will be answered and protocoled. Finally, we will assess and publish reproducibility during the practice session.
- (3) The workload of a resident highly depends on the number of patients in his charge, day of observation, and backlog of administrative task. To minimize this, we will randomize the shifts to be observed, with stratification to the day of the week.
- (4) We are already aware of the results of the "before" observation. We might therefore misguide observers towards the expected outcomes. During the study period, the observers and the investigator will be blinded to the results. A single designated investigator will check and process collected data to avoid IT issue.
- (5) Residents may misinterpret the present study as a way for the management to check their duty hours and then retaliate, despite the assurance of anonymization. This misunderstanding could lead to major modifications in the behaviour of some residents but it will not be possible to assess in what way: would they stay later on purpose or, on the contrary, end at the official time? We will mitigate this risk by designing an external and neutral person as "ombudsman".
- (6) The design of our study is based on a consistent observation on both before and after groups. Nevertheless, we considered the implemented reforms as interventions and chose outcomes described in the present protocol afterwards. We may thus have eliminated unfavourable outcomes.

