Method: We will use a before and after design, comparing residents' activities during shifts with time and motion studies. We will include all residents working on the internal medicine ward in Lausanne University Hospital. The before group was observed in 2015 and results are already published. The after group will be observed in 2018, using the exact same methods and tools. The intervention is made of major reforms implemented between 2016 and 2017, which will be reported in detail. The primary outcome will be time spent for administrative tasks. We will also measure the amount of task switching per hour, the mismatch between observed activities compared to the departmental work schedule, the effective duration of observed shifts, and the time spent in presence of patients. We added a qualitative part by means of focus groups composed of observed residents.

Results and expected benefits: We already have 697 hours of observation on the before group. For the after group, we expect to include 35 residents. Each resident being observed twice, we will gather between 700 and 900 hours of observation. Based on our previous study, this number will be sufficient to show a significant reduction of 20 % of administrative tasks (20 minutes per shift). A significant reduction of administrative burden will give an objective assessment of the impact of our reforms but will also confirm the options we took to develop the framework for future young residents and keep hospital internal medicine attractive. Such a time-and-motion study, which has been already replicated in another hospital, is a consistent base for auditing workplace quality, compared to other quality indicators like the average length of stay of patients.

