Candidates will have to learn description of activities based on an e-learning at home, using a web-based flashcard application. Investigators will train observers during a common half-day, within a few weeks before study. During the training, a standardized 1-hour video will be broadcasted and coded by the candidates. Selection will be based on reliability of video coding. After selection, each observer will follow a resident during a half-day, as blank observation. During a dedicated meeting, the observers will have the opportunity to ask questions, identify difficulties and get feedback. We will gather questions and answers in a document distributed to the observers.

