10 APPENDICES

- **Appendix 1** Description of the 22 possible activities of the resident, that an observer may record using the dedicated tablet application.
- Appendix 2Politique de sécurité des systèmes d'information des hospices / CHUV. Hospices-CHUV.
Direction générale. 26.08.2005 (available upon request)
- **Appendix 3** Exigences de sécurité des systèmes informatiques. 02.03.2016 (available upon request).

Appendix table 1. Description of the 22 possible activities of the resident, that an observer may record using the dedicated tablet application. * Activities considered as administrative tasks for the primary outcome.

Category	Activity	Description					
Directly related to patients	Admission	Anamnesis, clinical examination, and communication with the patient. Starts when the resident is looking after a new patient.					
	Patient rounds	Daily medical round of inpatients the resident is in charge of: EMR review, anamnesis, clinical examination, prescription of treatments, and orders. Also includes daily sign-out round at the nursing desk.					
	Patient discharges activities	Preparation for patient discharge: Prescription writing, last interview with the patient, and delivery and explanation of prescription.					
	Clinical procedures	All medical procedures performed by the resident on a patient, including but not limited to arterial blood gas testing and punctures (e.g., ascites, lumbar, or pleural).					
	Out of unit support	Attendance of the resident alongside the patient outside the ward: Oversight during examinations, transfer to another department, and emergencies.					
Communication	News delivery	Bad news or therapeutic orientations that need a specific additional interview and patient educational therapy.					
	Family meeting	Communication with family, close relatives, or nonprofessional caregivers. Time for providing information, explanation, and collecting information and opinions.					
Indirectly related to patients	Looking for information *	Looking for information in the paper record, EMR, computer archives, or other medical record. Excludes admission activity.					
	Literature review	Looking for scientific data to improve/determine patient management, including medical textbooks, scientific papers, and Web sites.					
	Writing in medical record	Writing notes, problems list, handoffs, or examination results. Excludes admission activity and discharge report.					

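### The blind in Protocol 4.8(4) covers undefined results and does not reach the knowledge that the same item names as the source of bias

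*Protocol*

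**What the plan says.** Section 4.8(4) of the Protocol states that the team knows the 2015 results and draws the consequence: "We might therefore misguide observers towards the expected outcomes". The remedy follows directly: "During the study period, the observers and the investigator will be blinded to the results". One designated investigator then checks and processes the collected data, for a stated technical (IT) purpose.

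Other sections bear on whether that remedy works:

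- The abstract says of the baseline: "The before group was observed in 2015 and results are already published". Section 6 adds that the publication drew lay-media interest.
- Section 4.5.1 says: "Investigators will train observers during a common half-day, within a few weeks before study". It adds that the team compiles coding questions and answers and hands them to the observers. Section 4.8(2) says that "each dubious interpretation of activities will be answered and protocoled", without naming who answers.
- Section 4.7.1 fixes the expected direction, a reduction in administrative time. Section 4.7 tests it one-sided at 0.05.
- Section 4.1.1 defines the primary outcome as the sum of four activities. Appendix table 1 marks them with an asterisk, explained as "Activities considered as administrative tasks for the primary outcome".

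**The concern.** The item names a cause (knowledge of 2015 and of the hoped-for change) and a route (investigators influencing observers). The countermeasure is a blind to something left undefined, and on neither reading does it remove the cause.

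The primary outcome is a sum of times that observers assign by judgement to one of 22 exclusive codes. The 2015 data were collected before any reform had begun (section 4.2.1), so an expectation that the reforms had helped could act only on the 2018 side. It would act in the direction of the one-sided test. A modest tendency to resolve doubtful acts away from the four outcome codes would look like a benefit of the reforms.

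**Working it through.** **Step 1. The two readings of the results.**

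- *The 2015 results.* Investigators cannot be blinded to them, since the same item says they know them. Newly recruited observers could be, though only partly, because the paper is public.
- *The accruing 2018 results.* This closes one real route: seeing interim figures and then correcting observers. It leaves the 2015 figures and the expected direction known to those who train the observers.

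**Step 2. Does the blind cover the training?** It applies during the study period. Table 4 puts the half-day training on 01.05.2018 and starts the study time on 14.05.2018, which would leave training outside it. The synopsis gives May to August 2018, which would include it. The text does not settle this.

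**Step 3. What observers are told.** No section says that they are kept from the hypothesis, the 2015 figures or the make-up of the primary outcome. No section says that they are given these either.

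**Step 4. Is there room for judgement?** Booking appointments is listed under patient administrative tasks, which count towards the outcome (section 4.1.1). Booking an appointment is also listed under talking with providers/collaborators, which does not (Appendix table 1). One act can fall on either side.

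**Step 5. Scale.** Inputs: 697 hours observed in 2015 (abstract); 66 observations, 92 administrative minutes per dayshift and a 20-minute target effect (section 4.7.2).

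- Average observed shift: 697 × 60 / 66 = 634 min.
- Target as a share of the shift: 20 / 634 = 3.2%.
- Target as a share of administrative time: 20 / 92 = 21.7%.

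The second share is the more telling, because the misassigned minutes must come out of the 92. The 634 minutes also average over all observed shifts, day and evening, whereas the 92 is per dayshift.

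**Step 6. Smaller shifts (illustration).** Assume no true effect, an SD of 36 min (section 4.7.2 calls this figure a standard error; it is treated here as an SD), independent observations, and a fraction f of the 92 minutes coded outside the outcome in 2018. The one-sided false-positive rate is Φ(92f / (36 × √(2/n)) − 1.645), with n per period.

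| f | Minutes | n = 36 | n = 66 |
|---|---|---|---|
| 0 | 0 | 5% | 5% |
| 5% | 4.6 | 14% | 18% |
| 10% | 9.2 | 29% | 43% |
| 20% | 18.4 | 70% | 90% |

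For example, with f = 10% and n = 36: 9.2 / 8.485 = 1.084; 1.084 − 1.645 = −0.561; Φ = 0.288. The fractions are assumptions, and the protocol gives no figure for f.

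**The case against.** The protocol discloses this bias itself, and an uncontrolled before-after study cannot mask the period. It commits to the 2015 method for recruiting and training observers, for activity definitions and for data collection (section 4.2.1). Observers are selected on reliability in coding a standard video, codes are timestamped in real time, and reproducibility will be published. Routing the data through one investigator may be what lets the others stay blind to the 2018 data. And more than a fifth of administrative time would have to be misassigned, net and in one direction, to produce the whole effect.

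Much of this stands. These safeguards limit discretion, but they address misclassification in general, not coding that leans one way.

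A reader might infer several stronger points that the protocol does not support:

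- *Investigators who know the 2015 figures decide every doubtful code.* Who answers is not stated. The text says only that investigators train observers and that the team distributes the answers.
- *The designated investigator can recode data towards the hypothesis.* The stated purpose is technical, and no recoding is described.
- *Observers learn from the starred table.* Section 4.5.1 says that they learn activity descriptions by e-learning with flashcards. The asterisks are shown only in the protocol's appendix.
- *Only a trivial 3% of time need move.* That share uses the whole shift as denominator; it is about 22% of the administrative minutes.

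**Conclusion.** The point holds as a fault in the wording and reach of section 4.8(4). The item states a blinding rule that misses its own target: it cannot hold for investigators if it means the 2015 results, and it leaves the expected direction known if it means the 2018 results. What observers are told about the hypothesis and the outcome is left unstated, where at least one act straddles the outcome's boundary.

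A net shift of about 20 of 92 minutes would mimic the full target effect, and smaller shifts would bias the comparison proportionately. The false-positive rates above rest on an SD of 36 min, independent observations and assumed fractions. They show sensitivity only, and nothing in the protocol shows that such bias will occur. This is a cheap improvement, not a defect that invalidates the design.

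**What to change.** Reword section 4.8(4) to say that, until observations end:

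1. Observers are not told the expected direction, the 2015 figures or which activities make up the primary outcome. Their training material carries the 2015 activity definitions without the asterisks.
2. The coding question-and-answer document is closed after the post-training meeting and before the first observation on 21.05.2018. No new rulings are made afterwards on any activity; covering all activities avoids signalling which ones count.
3. The results are defined as the 2015 figures for observers, and as the accruing 2018 data for observers and all investigators except the designated data processor.

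This fits the commitment to the 2015 method: section 4.8(6) says that this study's outcomes were chosen afterwards, so the 2015 observers could not have been coding with them in mind.

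The cost is protocol wording and an edited training sheet. Table 4 gives no date for the post-training meeting, and blank observations run to 18.05.2018, so the meeting needs a slot before 21.05.2018. There are two downsides: the blind is partial because the 2015 paper is public, and coding doubts that arise later must be settled from the written definitions alone.

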4.9 Safety

No safety issue is associated with the present protocol.

5 ETHICAL AND REGULATORY ASPECTS

In 2015, for our baseline study, the local ethical committee certified that no protocol approval was required, arguing the absence of intervention or collection of data on patients. The present study will use the same design but we will still renew the request to the local ethical committee. We will inform all participants during a dedicated meeting. Presentation support will be kept available. We will ask for written consent before the randomization of observation. We will not disclose the identity of residents refusing consent to the management. No patient identity nor other characteristic will be recorded during the study. Observers are legally bound to confidentiality as mentioned in al 2, art 321 and art 321bis CP.

5.1 Conflict of interest

None.

6 COMMUNICATION OBJECTIVES

Based on the 2015 baseline study experience, we will communicate the results as follows:

- (1) **SSMIG-Foundation**: We will first send an intermediate report to the SSMIG-Foundation with the preliminary results, including the description of interventions indicated in section 4.4.
- (2) Specialty congresses: We will submit the content of the report as an abstract to the SSMIG annual meeting. Preliminary results will be communicated in internal medicine congresses like SSMIG, ECIM, ACP Congress, and others. We expect to present several posters and/or oral presentations.
- (3) **Scientific publications**: We will submit the main results to a high impact factor journal; the first target journal will be *Annals of internal medicine*. We also expect to submit at least two other manuscripts, either as a full article or as a short communication. The focus group results will be published apart and in more details. Clinical governance and human resources aspects will also be addressed.

Subject	Туре	Journals (example)
Main article : primary and secondary outcomes	original research	Ann Int Med
Results of focus group : comments and expectations of residents	full article	Eur J of IM
Correlation of localisation and activities	short report	BMJ quality and safety
Ward rounds : in/out of the room	full article	BMC Med Educ
Comparison with other hospitals, after replication studies (see below).	full article	Swiss med wlky

Table 3. Publication plan

- (4) **Quality and clinical governance networks**: We will share our work through several groups as: *Quality Improvement in Swiss Primary and Hospital Care* or *Académie suisse pour la qualité en médecine*.
- (5) Lay media: Our publication in Annals of internal medicine reached the top 5% of all research outputs scored by Altmetric (2017) and received a clear interest in local (www.letemps.ch, www.nzz.ch) and international (www.foxnews.com) non-scientific media. A collaboration with the media relations group of the CHUV will be established: multilingual press releases will be issued jointly and sent to interested media upon publication of the main results; whenever possible, the media channels of the scientific journals will be solicited to increase public visibility of our findings. Short communications will be also published in the social network accounts of the CHUV, and interviews or press conferences if requested will be given in close relationship with the media relations group of the CHUV.
- (6) **Replication studies**: Baden hospital replicated our 2015 baseline study in 2017.(Frey *et al.*, 2017) We will continue to encourage replication studies in Switzerland and abroad, by freely transferring tools and methods.

7 STUDY SCHEDULE

Table 4 and **Figure 1** present the study schedule. To avoid bias related to the beginning and end of rotations, and seasonal variation of activity, it is absolutely mandatory to match the period of observations (\star) with the 2015 baseline study. Therefore, we will prepare the study until the "point of no return" (\star). In the absence of funding, the study will be postponed to the following year.

Tasks	Start	End			
Preparation	01.01.2018	11.05.2018			
Protocol preparation	01.01.2018	27.02.2018			
Protocol submission	28.02.2018	28.02.2018			
Ethical committee approval	05.03.2018	27.04.2018			
IT tools preparation	05.03.2018	11.05.2018			
Tablet application	05.03.2018	27.04.2018			
Building observers team	09.04.2018	18.05.2018			
Recruitment of observers	09.04.2018	26.04.2018			
Pre-selection of candidates	27.04.2018	27.04.2018			
E-learning	27.04.2018	30.04.2018			
Half-day training (all candidates together)	01.05.2018	01.05.2018			
Selection of observers	02.05.2018	02.05.2018			
Point of no return (no fund, no study) →	07.05.2018	07.05.2018			
Half-day blank observation (one per observer)	07.05.2018	18.05.2018			
Study time	14.05.2018	31.08.2018			
Randomization of days of observation	14.05.2018	18.05.2018			
Observations *	21.05.2018	20.07.2018			
Focus group	30.07.2018	31.08.2018			
Analysis	23.07.2018	31.12.2018			
Processing of data	23.07.2018	24.08.2018			
Focus group analysis	03.09.2018	28.09.2018			
Statistical analysis	27.08.2018	21.09.2018			
Description of intervention	24.07.2018	28.09.2018			
Writing	01.10.2018	31.12.2018			
Communication	03.12.2018	30.05.2019			
Intermediate report to SSMIG-foundation	03.12.2018	31.12.2018			
Presentation and publication	01.01.2019	30.05.2019			

Table 4. Detailed study schedule with milestones. IT: Information technologies.

[figure not shown]

Figure 1. Gantt chart for study plan.

8 BUDGET ESTIMATION

Table 5 presents the forecasted expenses and incomes of the study. The data of the 2015 baseline study are available without additional charge.

					Inco	mes				
Item	Amount and rate	Exp	Expenses		Expenses				SSMIG- foundation	
				fu	nding	tou	ndation			
Cost of observer labour: Day hours 6 am to 8 pm) Special hours (8 pm to 6 am)	24 CHF / hour 31 CHF / hour									
Half-day training Half-day blank observations	4 hours 8 hours									
Number of observers	5 to 8									
One day shift One evening shift	11 to 15 hours 4 h and 3 to 5 special h									
Number of observed shifts	70 (2 x 35)									
Total day hours	50 * (11 to 15) + 20 * (4) + 12 * (5 to 8) = 690 to 926 hours	CHF	22'220			CHF	22'220			
Total special hours	20 * (3 to 5) = 60 to 100 hours	CHF	5'020			CHF	5'020			
Project manager	3 months, part time	CHF	10'000	CHF	7'000	CHF	3'000			
Dactylography skill test	35 * 30 CHF	CHF	1'050			CHF	1'050			
Recording device (tablet)	4 * 400 CHF	CHF	1'600			CHF	1'600			
Preparation of tablet application		CHF	5'000	CHF	5'000					
Devices for localization (beacons)	50 * 50 CHF + 500 CHF	CHF	3'000			CHF	3'000			
Focus group manager		CHF	12'000	CHF	7'000	CHF	5'000			
Statistician fee	50 * 120 CHF	CHF	6'000	CHF	6'000					
Publication fee provision		CHF	2'000			CHF	2'000			
Communication, transport, posters		CHF	1'000			CHF	1'000			
Overhead	(15%)	CHF	9'110	CHF	3'000	CHF	6'110			
Total		CHF	78'000	CHF	28'000	CHF	50'000			

Table 5. Estimation of expenses and incomes for the study.

